10.2 Descriptive statistics

Variables are described using the parameters for central tendency and spread as displayed in Table 5, p65.

Scale:	Distribution:	Central Tendency:	Spread:
Continuous	Normal	Mean	95%-CI or full range
	Lognormal	Mean*	95%-CI*or full range*
	Not-normal	Median (=p ₅₀)	IQR or full range
Categorical	Binomial	Percentage	Exact Clopper-Pearson (β- distribution)

Table 5: Handling of descriptive statistics. *parameters are estimated on the logtransformed variable and back-transformed. 95%-CI: 95%-confidence interval using normal distribution (mean \pm 1.9600 x standard deviation). IQR: interquartile range (p₂₅ and p₅₀).

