2.2.3 Secondary Objective 3: Costs and Cost-Effectiveness

- SO3a: To determine the effect of incorporation of FDG-PET/CT on the mean direct costs (=volume of care multiplied by activity-based costs) per patient during the first 12 months after FDG-PET/CT.
- SO3b: To determine the effect of incorporation of FDG-PET/CT on the average length of hospital stay for treatment of (complications of) thyroid lesions?
- SO3c: To determine the total number of sick leave days for the first three months in the patients (recall, supported by 2 questionnaires)? Do these differ between both study arms?
- SO3d: To determine the incremental Net Monetary Benefit of incorporation of FDG-PET/CT with respect to QALYs (based on EQ-5D-5L index and overall survival) saved including sensitivity analysis.
- SO3e: To determine the incremental Net Monetary Benefit of incorporation of FDG-PET/CT with respect to decrease in unbeneficial treatment. Sensitivity analysis will be performed.
 A mere description will be given as there is no "accepted" value for this kind of analysis.

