3. STUDY DESIGN

A partially-blinded, prospective, multi-centre, block-randomised controlled trial (RCT) is designed. After obtaining written informed consent, patients are registered centrally, FNAC is reviewed centrally and thereafter patients are randomised to either the experimental study-arm (arm A: FDG-PET/CT driven management decisions) or a control study-arm (arm B: surgery regardless FDG-PET/CT result) using a 2:1 allocation ratio. The latter is performed both for methodological purposes (the treatment of the subjects in the control study arm is well investigated and described before) and to satisfy the assumption that patient prefer the experimental study-arm. The result of randomization is blinded to the treating physicians and central FDG-PET/CT review committee. Allocation is adaptively stratified using the minimisation method on the centre of inclusion and the most prognostic features of DTC known at this stage of patient work-up: (US) lesion size (0-10 mm/11-20 mm/21-40 mm/40+ mm), patient sex, patient age (<45yr, \geq 45yr) and Bethesda classification according to central review committee (atypia of unknown significance/follicular lesion of unknown significance (III) or (suspicion) for a follicular neoplasia (IV)).

Based on the study arm allocation and PET result, treating physicians will either be told to cancel scheduled diagnostic thyroid surgery (allocation to the experimental arm with a negative FDG-PET/CT at central review or ~32/132 patients) or to proceed with surgery (all other cases or 100/132 patients). In case surgery is cancelled the patients need to be followed-up by watchful waiting and a confirmatory ultrasonography (including FNAC) after 12 months. Patient allocation will not be disclosed to prevent study withdrawal, however in case surgery is cancelled unblinding is unavoidable (~25% of all included patients).

The Gold Standard is histology, revised by a (central) dedicated pathologist panel, obtained from surgery or 12-months follow-up, including US (+FNAC). All patients will be followed for at least 12 months after FDG-PET/CT to ensure all direct costs and complications are noted. Five years after inclusion of the last patient, long-term follow-up will be determined based on patient file review and contact with the general practitioner (flowchart Figure 1, p34 and

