10. STATISTICAL ANALYSIS

10.1 General remarks

All (statistical and economical) analyses will be supported by epidemiologists and biostatisticians from the LUMC.

All continuous data (e.g. age, FDG-PET/CT standardised uptake level (SUV), volumes of care, hospitalisation and sick leave days, Tg-level, questionnaire scores, etc.) will be assessed for (log)normality.

All categorical data (e.g. sex, FDG-PET/CT positive or negative, malignant or benign, histology, etc.) are treated as either ordinal or nominal.

One year is defined as 365.242199 days. Age, overall survival, disease-free-survival are computed with respect to the date of the (last) US guided FNAC that led to study enrolment. Survival is computed, using the Kaplan-Meier method, taking into account censored data (censored to the date of last follow-up or death (for all but overall survival)). For comparison of Kaplan-Meier estimates, the logrank statistic will be used (as the Breslow and Tarone-Ware tests are better used when the data does not fulfil the proportional hazards assumption; they are both weighted versions of the logrank test giving extra weight to events happening earlier on. The Tarone-Ware has slightly less extreme weightings. Both should be avoided in case of a high level of censoring or unequal censoring between groups).

All prices will be calculated based on national price levels (in Euro, €), indexed to the year of first patient inclusion (2015). Price-index-numbers will be used to account for price changes during the years of patient inclusion and follow-up. In case of costs distributed over several years, net present values are computed using a constant 4% discount rate and effects using a constant 1.5% discount rate, which is a common method in the Netherlands (other countries usually use uniform discounting). For all computations, the methods for cost-research of Hakkaart-vanRoijen et al.[68] will be used.

Missing values will not be completed by any means (e.g. average). In case of missing values, the fraction missing values will be stated. Multivariate analysis might therefore only be performed on a subset of patients (without missing values in all independent parameters), however due to the nature of the important independent parameters, we expect that this "subset" of patients will be over 95% of the study population.

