10.3 Univariate analysis

All comparisons will be made using the general requirements for relating research questions as stated in Table 6, p66.

Characteristics of (independent) study-arms will be compared using either t-tests ((log)normal) or Wilcoxon rank-sum tests for continuous variables (e.g. age, SUV, hospitalisation days, volumes of care used, questionnaire scores). For categorical data either Fisher exact tests or χ^2 tests will be used (e.g. sex, unbeneficial patient management).

With respect to the primary research question, fractions unbeneficial patient management therefore will be compared using Fisher exact tests or χ^2 tests.

Relations between variables will be univariately described by the parameters from Table 7, p66. These parameters are compared using the tests from Table 8, p67.

Scale:	Groups:	Dependency:	Group Size:	Distribution:	Test:
Continuous	1	n/a	n≥30	(Normal)	t-test
(and			n<30	Normal	_
categorical ordinal)				Not normal but transformable	Transform than t-test
				Not normal, not transformable	Sign test
	2	Independent	n≥30	(Normal)	t-test
	-	n<30		Normal, equal variances	
				Normal, non-equal variances, equal n's	-
				Normal, non-equal n's, transformable	Transform than t-test
				Normal, non-equal variances, non-equal n's, not transformable	Wilcoxon rank-sum tes (= Mann-Whitney U test
				Not normal, transformable	Transform than t-test
				Not normal, not transformable	Wilcoxon rank-sum tes (= Mann-Whitney U test
		Dependent	n≥30	(Normal)	Paired t-test
			n<30	Normal	_
				Not normal, transformable	_
				Not normal, not transformable	Wilcoxon signed ranks
	≥3	Independent	n/a	Normal, 1 factor	One-Way ANOVA
				Normal, ≥2 factors	Two-Way or othe ANOVA
	_		Not normal	Kruskal-Wallis for Factor (+Dunn's posthoo test)	
		Dependent	n/a	Normal	Repeaed Measures
				Not normal	Friedman ANOVA
Categorical (Nominal)	1		np≥5 and n(1- p)≥5		z-approximation
	2	Independent	Expected cell frequencies <5		Fisher's Exact Test
≥3	_		Expected cell frequencies ≥5		X ² or z-approximation
		Dependent			McNemar or ĸ
	≥3	Independent	Expected cell frequencies <5		Collapse categories fo X^2
			Expected cell		X ²
			frequencies ≥5		

Table 6: General Requirements for selection of Statistical tests used for univariate analysis (comparison)

Predicting each other	Parameter:
	Relative Risk
	Spearman's ρ squared
yes	Regression
no	Pearson's Correlation R squared (log)normal
	Spearman's p squared (not-normal)
	yes

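### Table 5 would summarise hospital days by a median, which need not reflect the change in average stay that SO3b asks for

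*Protocol*

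**What the plan says.** Section 10.1 lists the continuous variables and their common treatment: "volumes of care, hospitalisation and sick leave days, Tg-level, questionnaire scores, etc.) will be assessed for (log)normality". Section 10.2 ties the summary to the outcome of that check: "Variables are described using the parameters for central tendency and spread as displayed in Table 5". Table 5 has three rows for continuous data. Normal data get a mean, lognormal data a starred mean, and all other data a median with the IQR or full range. The footnote explains the star: "parameters are estimated on the logtransformed variable and back-transformed".

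Section 10.3 compares the arms by t-tests or by "Wilcoxon rank-sum tests for continuous variables (e.g. age, SUV, hospitalisation days, volumes of care used, questionnaire scores"). Table 6 in that section assigns a t-test to two independent groups of 30 or more.

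The objective served is SO3b in section 2.2.3: "To determine the effect of incorporation of FDG-PET/CT on the average length of hospital stay". Its neighbour SO3a asks for "mean direct costs (=volume of care multiplied by activity-based costs) per patient during the first 12 months".

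Section 3 says whose surgery is cancelled: "allocation to the experimental arm with a negative FDG-PET/CT at central review or ~32/132 patients".

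**The concern.** The PET strategy is meant to save hospital days by leaving some patients unoperated. Its effect on this variable is therefore a block of zeros in arm A, with the remaining stays much as they were. An arithmetic mean over all patients counts every zero in proportion. A median does not: while fewer than half of arm A has a zero, the median is some value among the operated patients, and how far it moves depends on how tightly their stays cluster.

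The (log)normality rule thus replaces the quantity named in the objective with one that does not measure days saved. At stake is the effect size reported for SO3b, a secondary result that informs the resource-use argument.

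**Working it through.** **Inputs.** Pooled counts from section 1.3 and Appendix IV: 225 patients, of whom 83 PET-negative (3 malignant) and 142 PET-positive (55 malignant, 87 benign). Arm sizes from section 4.4: 88 (A) and 44 (B). Section 1.1 says that most malignant nodules need a second operation. Assumptions: one admission per operated patient, a second if malignant, and none for PET-negative patients in arm A. The protocol gives no lengths of stay.

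**1. The plan's own figure.** 88 × 83/225 = 32.5 patients, and 32.5/132 = 24.6%. This reproduces the roughly 32 of 132 in section 3. Within arm A the share of zeros is 83/225 = 36.9%.

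**2. Mean admissions per patient.**
- Arm B: (167 × 1 + 58 × 2)/225 = 283/225 = 1.258.
- Arm A: (83 × 0 + 87 × 1 + 55 × 2)/225 = 197/225 = 0.876.
- Fall: 1 − 197/283 = 30.4%.

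Counting only the first admission, the fall is 1 − 142/225 = 36.9%. With a third admission for radio-iodine in each operated malignancy it is 1 − 252/341 = 26.1%. If days per admission have the same distribution in both arms, mean days fall by the same percentages.

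**3. Where the arm A median lies.** With 36.9% zeros, it sits at the (0.5 − 0.369)/(1 − 0.369) = 0.131/0.631 = 0.21 quantile of the operated patients' days. The arm B median is at their 0.50 quantile. If stays are tightly clustered, these two quantiles coincide.

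**4. Mean and median under four assumed stays** (arm B → arm A; means, and the lognormal medians, from large simulated samples).

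| Days per admission | Mean | Fall | Median | Fall |
|---|---|---|---|---|
| 2 for everyone | 2.52 → 1.75 | 30% | 2 → 2 | 0% |
| 1 to 5, with 15/55/20/6/4% | 2.88 → 2.01 | 30% | 2 → 2 | 0% |
| 1 to 5, with 35/40/15/6/4% | 2.57 → 1.79 | 30% | 2 → 1 | 50% |
| Lognormal, median 2, log-SD 0.5 | 2.86 → 1.99 | 30% | 2.44 → 1.62 | 33% |

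The jump between the second and third rows can be checked by hand. If a share s of admissions lasts one day, the proportion of arm A with at most one day is (83 + 87s)/225. This passes one half when s > (112.5 − 83)/87 = 0.34. At s = 0.15 it is 0.427 and the median is 2; at s = 0.35 it is 0.504 and the median is 1. The mean falls by about 30% in both cases.

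**5. The planned tests.** In 4,000 simulated trials of 44 versus 88 (two-sided 0.05), an unequal-variance t-test on the raw days rejects in 96%, 83%, 75% and 73% of runs for the four rows in order. The Wilcoxon test rejects in 87%, 85%, 87% and 85%.

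**The case against.** Much can be said for the plan.

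- Table 5 is descriptive. For arms of 88 and 44, Table 6 leads to a t-test, and even after the 15% data loss allowed in section 4.4 the smaller arm keeps 44 × 0.85 = 37 patients. That test compares means, and step 5 shows that it or the Wilcoxon test would usually find the difference. This stands: a reader might infer that the trial would miss the effect, and the figures do not support that. But a p-value does not give the size of the effect, and a significant difference in means could be published beside two identical medians.
- Table 5 pairs the median with the IQR or full range. With 37% zeros, the lower quartile and the minimum in arm A are both 0, so the unoperated patients remain visible. This also stands, although a reader still could not recover the average saving from those figures.
- Costs are not distorted. SO3a asks for means itself, and section 10.6 multiplies volumes by prices per patient and uses bootstrap or Fieller methods for the cost-effectiveness ratio. One might carry the argument over to direct costs or net monetary benefit, but section 10.6 does not route those through Table 5.
- The excess of zeros is shown for hospital days only. The protocol gives no distribution for sick leave, and unoperated patients still use outpatient care.
- SO3b does not state its denominator, and length of stay is often quoted per admission. The reading per patient rests on the Summary, which expects hospitalisation to fall because surgery is avoided, and on the per-patient volumes in section 10.6. The open denominator is a further reason to write it down.

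**Conclusion.** The point holds in a limited form. For hospitalisation days, the rule in sections 10.1 and 10.2 leads to a median where SO3b asks for an average. A fall of about 30% in the mean (26% to 37% over the admission counts tried) can appear as no change or as a fall of up to about 50% in the median across the stays tried. The summary then depends on how stays cluster rather than on days saved. This rests on the protocol's pooled PET results, on the assumed admissions per malignancy, and on assumed lengths of stay.

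Two stronger readings are not supported. The first is that the summary will show no effect: that happens only when stays are tightly clustered. The second is that the log row of Table 5 would drop the zeros and reverse the direction of the effect. A variable with this many zeros would not pass as lognormal, the protocol nowhere says that zeros are removed, and section 10.1 requires intention-to-treat analysis. The sound conclusion about that row is only that it cannot be used with zeros.

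This is a correction to the reporting of a secondary outcome. It leaves the primary analysis and the cost-effectiveness analysis untouched.

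**What to change.** In sections 10.1 and 10.2, exempt hospitalisation days from the distribution-based choice of summary. State that they are reported for each arm as the arithmetic mean per patient over all randomised patients with data, with an unoperated patient's zero counted as an observed value. Give the difference in means between arms with a bootstrap confidence interval, a method that section 10.6 already names. Keep the median and IQR as supplementary description. Apply the same wording to sick-leave days and volumes of care, for consistency across the SO3 objectives.

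The cost is about one sentence in the analysis section. No new data, visits or patients are needed.

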10.3 Univariate analysis

All comparisons will be made using the general requirements for relating research questions as stated in Table 6, p66.

Characteristics of (independent) study-arms will be compared using either t-tests ((log)normal) or Wilcoxon rank-sum tests for continuous variables (e.g. age, SUV, hospitalisation days, volumes of care used, questionnaire scores). For categorical data either Fisher exact tests or χ^2 tests will be used (e.g. sex, unbeneficial patient management).

With respect to the primary research question, fractions unbeneficial patient management therefore will be compared using Fisher exact tests or χ^2 tests.

Relations between variables will be univariately described by the parameters from Table 7, p66. These parameters are compared using the tests from Table 8, p67.

Scale:	Groups:	Dependency:	Group Size:	Distribution:	Test:
Continuous	1	n/a	n≥30	(Normal)	t-test
(and			n<30	Normal	_
categorical ordinal)				Not normal but transformable	Transform than t-test
				Not normal, not transformable	Sign test
	2	Independent	n≥30	(Normal)	t-test
	-	n<30		Normal, equal variances	
				Normal, non-equal variances, equal n's	-
				Normal, non-equal n's, transformable	Transform than t-test
				Normal, non-equal variances, non-equal n's, not transformable	Wilcoxon rank-sum tes (= Mann-Whitney U test
				Not normal, transformable	Transform than t-test
				Not normal, not transformable	Wilcoxon rank-sum tes (= Mann-Whitney U test
		Dependent	n≥30	(Normal)	Paired t-test
			n<30	Normal	_
				Not normal, transformable	_
				Not normal, not transformable	Wilcoxon signed ranks
	≥3	Independent	n/a	Normal, 1 factor	One-Way ANOVA
				Normal, ≥2 factors	Two-Way or othe ANOVA
	_		Not normal	Kruskal-Wallis for Factor (+Dunn's posthoo test)	
		Dependent	n/a	Normal	Repeaed Measures
				Not normal	Friedman ANOVA
Categorical (Nominal)	1		np≥5 and n(1- p)≥5		z-approximation
	2	Independent	Expected cell frequencies <5		Fisher's Exact Test
≥3	_		Expected cell frequencies ≥5		X ² or z-approximation
		Dependent			McNemar or ĸ
	≥3	Independent	Expected cell frequencies <5		Collapse categories fo X^2
			Expected cell		X ²
			frequencies ≥5		

Table 6: General Requirements for selection of Statistical tests used for univariate analysis (comparison)

Predicting each other	Parameter:
	Relative Risk
	Spearman's ρ squared
yes	Regression
no	Pearson's Correlation R squared (log)normal
	Spearman's p squared (not-normal)
	yes

 Table 7: Parameters describing association between variables.

Statistic:	Number		
Correlation Coefficient (R)	1	R=0?	t-test
		R=value	Fisher's z Transformation
	2	Independent	
		Dependent	
Regression Coefficients	1		t-test
	2		

 Table 8: Comparison between parameters describe association

Se, Sp, PPV and NPV will be computed using the traditional formulae, using the definition for true/false positive as described in Table 9, p67, §8.3, p48:

Sensitivity: $Se = \frac{TP}{TP+FN}$, $Specificity: Sp = \frac{TN}{TN+FP}$ Accuracy: $Acc = \frac{TP+TN}{TP+TN+FP+FN}$, $Prevalence: Prev = \frac{TP+FN}{TP+TN+FP+FN}$ Positive Predictive Value: $PPV = \frac{TP}{TP+FP}$, $Negative Predictive Value: NPV = \frac{TN}{TN+FN}$ Positive Likelihood Ratio: $LR + = \frac{Se}{1-Sp}$, $Negative Likelihood Ratio: LR - = \frac{1-Se}{Sp}$ Diagnostic Odds Ratio: $dOR = \frac{LR+}{LR-}$, $SE(LOG(dOR)) = \sqrt{\frac{1}{TP} + \frac{1}{TN} + \frac{1}{FP} + \frac{1}{FN}}$ [69]

	Disease +ve	Disease –ve
Test +ve	TP	FP
Test –ve	FN	TN

Table 9: Definition of true positive (TP), true negative (TN), false-positive (FP) and false-negative (FN).

Threshold effects of FDG-uptake in de nodules will be assessed using receiver-operating characteristic (ROC) curves and quantified using the area under the curve (AUC), as Se and Sp are inversely related. The standard error (and thus the 95%-CI) of the AUC can be computed either under a bi-negative exponential assumption (used only when the number of positive actual states is equal to the number of negative actual states) or using a non-parametric assumption (used in all other cases).

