Rationale: Only about ¹/₄ of patients with thyroid nodules with indeterminate cytology are proven to suffer from a malignancy at diagnostic hemithyroidectomy. Therefore $\sim \frac{3}{4}$ is operated upon unbeneficially. Recent studies using FDG-PET/CT have suggested that it can decrease the fraction of unbeneficial procedures from ~73% to ~40%. Thereby the direct costs per patient, the number of hospitalization and average sick leave days might decrease and the experienced HRQoL might increase. A study will be undertaken to show the additional value of FDG-PET/CT after indeterminate cytology with respect to unbeneficial procedures, costs and utilities. Main objective: To determine the impact of FDG-PET/CT on decreasing the fraction of patients with cytologically indeterminate thyroid nodules undergoing unbeneficial patient management. Study design: A prospective, multicentre, randomised, stratified controlled blinded trial with an experimental study-arm (FDG-PET/CT-driven) and a control study-arm (diagnostic hemithyroidectomy, independent of FDG-PET/CT-result). Study **population:** Adult patients with a cytologically indeterminate thyroid nodule, without exclusion criteria, in 15 (university and regional) hospitals distributed over the Netherlands. Intervention: One single FDG-PET/low-dose non-contrast enhanced CT of the head and neck is performed in all patients. Patient management depends on allocation and results of this FDG-PET/CT. Main study parameters/endpoints: The number of unbeneficial interventions, i.e. surgery for benign disease or watchful-waiting for malignancy. For secondary objectives: complication rate, consequences of incidental PET-findings, number of hospitalisation and sick leave days, volumes of healthcare consumed, experienced HRQoL, genetic, cytological and (immuno)histopathological features of the nodules. Sample size calculation/data analysis: Based on above-mentioned estimated reduction in unbeneficial interventions from ~73% to ~40%, at least 90 patients with nodules>10 mm need to be analysed (2:1 allocation, α =0.05, power=0.90, one-tailed Fisher's exact test). After correction for nodule size and data-attrition, 132 patients need to be included in total. Intention-to-treat analysis will be performed. Incremental Net Monetary Benefit based on the total direct costs per patient and the gain in HRQoL-adjusted survival years are computed. Cytological, histological and genetic parameters and their correlation to FDG-avidity will be described. Nature and extent of the burden and risks associated with participation, benefit and group relatedness: All patients undergo one FDG-PET/CT scan of head/neck (effective dose: <3.5 mSv) and are asked to fill in 6 questionnaires at 4 time points. FDG-PET/CT negative patients in the experimental arm will undergo a single confirmatory US (±FNAC). An interim/posterior analysis of the control subjects is performed to ensure oncological safety. In case of an unexpected high false-negative ratio in this control arm, all patients will be advised to undergo surgery.

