4.4 Sample size calculation

Based on the main objective, it is expected that FDG-PET/CT can reduce unjust treatment from ~73.1% (=136/186 benign lesions >10mm) to ~40.3% (=75/186 false-positive and false-negative lesions >10mm, §1.3, p19). Using G*Power version 3.1.9.2. (and validated using JMP from SAS version 9.0.1, STATA version 12.0SE and PASS version 2011), we computed using an α error probability of 0.025 (=0.05/2, Bonferroni correction for interim analysis) a power of 0.80 and an allocation ratio of N_A:N_B=2:1, we need to include at least 90 patients in total (one-tailed test) to establish this difference (60+30 patients in arm A and B respectively).

Since around 82.7% (=186/225, §1.3, p19) fulfil the size criterion, at least 111 patients (74+37 patients in arm A and B respectively) need to be included. Accounting for additional 15% data loss at the final end-point, 132 patients should be included (88+44 patients in arm A and B respectively) (Figure 2, p40).

This total number of patients could at best (assuming no data loss) discern a reduction of 26.6% unjust treatment in the whole population with an actual α error probability of 0.016 and a power of 0.80. This is based on a reduction from 74.2% (prevalence of benign disease in all 225 patients) to 47.6%. In the experimental arm (88 patients), where the number of false-negative PET is estimated to be ~1.3% (3/225), this number of patients should establish a false-negative rate of maximal 7.5% (actual α error probability of 0.0066 and a power of 0.80). All analyses will be performed according to the intention-to-treat principle, meaning that analysis is based on the initial study-arm allocation and not on the treatment eventually received (e.g. a FDG-PET/CT negative patient in the experimental arm does not refrain from surgery and therefore actually is treated according to the control study arm).

[figure not shown]

Figure 2: Relation between study size (N), study-arm size sizes (n₁ and n₂) and effect size. Empirical relation: N=16.33935*ES^{-1.86986}, R²=.999443). Expected ES=73.1%-40.3%=32.8%

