8.2.2 Randomisation, stratification, blinding and treatment allocation

The prognosis of thyroid carcinoma is mainly determined by Metastasis, patient Age, Completeness of resection, local Invasion, and tumour Size (MACIS [52]). Apart from these properties, sensitivity of FDG-PET/CT is mainly determined by nodule size and specificity is mainly deteriorated by follicular origin of the nodule. Only age, nodule size (on ultrasonography), cytological subtype and sex are known at the time of inclusion (Table 4, p48). Recently it was described that lesions larger than 40 mm (T3) carry a higher risk of malignancy compared to smaller lesions (odds ratio: 2.10, 95%-CI: 1.26-3.50) and that men have a higher risk of malignancy than women (odds ratio: 1.51, 95%-CI: 1.20-1.83) [53]. We will use a minimisation strategy [54] to stratify for centre (site) of inclusion, US size, Bethesda subtype, Age and Sex only, meaning that in case patients are homogenously

distributed between both treatment arms over all these four factors, 2:1 randomisation will take place, in all other cases, patients will be allocated to the arm in which this type of patient is underrepresented.

Patients will be randomised in a 2:1 fashion to the experimental and control study arm. Patients, treating physicians, central pathologists and nuclear medicine physicians will be blinded for allocation, however in case of an FDG-PET/CT negative nodule in the experimental study arm, patient and treating physician are unblinded as surgery needs to be cancelled. In all other cases, patients proceed to surgery, but patients and treating physicians are kept blinded with respect allocation of the patient (either FDG-PET/CT positive nodule in the experimental study arm or inclusion in the control study arm regardless of PET-result).

EfFECTS

Factor:	Level 1:	Level 2:	Level 3:	Level 4:
Ultrasonographic	T1a (0-10mm)	T1b (11-20mm)	T2(21-40mm)	≥T3 (>40mm)
Nodule Size:	(13%)	(37%)	(37%)	(13%)
Bethesda Subtype	III (AUS/FLUS)	IV (SFN)		
	(67%)	(33%)		
Age	<45yr (40%)	≥45 yr (60%)		
Sex	Female (80%)	Male (20%)		

 Table 4: Stratification during study including expected fractions (based on [4] and [51]).
 AUS/FLUS: Atypia

 of Undetermined Significance or Follicular Lesion of Undetermined Significance; Rep: repeatedly; SFN: (Suspicious for) Follicular Neoplasm.

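### The primary test in §10.3 ignores the minimisation factors; it is valid and adequately powered, but should be adjusted to match allocation and backed by a supportive PET-negative comparison

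*Protocol*

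**What the plan says.** Protocol §10.3 compares the primary endpoint between arms without covariates: "fractions unbeneficial patient management therefore will be compared using Fisher exact tests", with χ² as the alternative. Table 6 in that section chooses between them by expected cell frequency, with 5 as the limit.

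The allocation is not simple randomisation. §3 states: "Allocation is adaptively stratified using the minimisation method on the centre of inclusion", followed by the main prognostic features known at entry. §8.2.2 gives the list as "to stratify for centre (site) of inclusion, US size, Bethesda subtype, Age and Sex only". Under that section, 2:1 randomisation applies only when patients are evenly spread over the factors. Otherwise the patient goes to the arm where that type of patient is under-represented, so allocation is largely deterministic. (§8.2.2 names five factors but then speaks of four, and Table 4 omits centre.)

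§10.4 allows multivariable models where appropriate. The outcomes it names are others, and it admits only variables with a significant univariate association. It does not adjust the primary comparison for the minimisation factors.

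PET is done in every patient whatever the allocation (§8.3.1). It is read by a committee blinded to allocation (§3). PET-positive patients in the experimental arm and all control patients proceed to surgery (§5.1).

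**The concern.** When allocation is forced to balance on prognostic factors, a test that ignores them overstates the standard error to the extent that the factors predict outcome. The usual remedy is to put the factors into the analysis by design, not by significance screening.

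A second feature of the design is also unused. Planned management differs between arms only for PET-negative patients. Among PET-positive patients any difference between arms should be chance, yet it adds noise to the crude comparison. With about 90 patients carrying the primary answer at a planned power of 0.80, it is worth asking how much precision each feature could return.

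**Working it through.** **1. The plan's own figure.** From §4.4: control rate 136/186 = 0.731, experimental rate 75/186 = 0.403, one-tailed α 0.025, power 0.80, "60+30 patients in arm A and B respectively". Full enumeration of the one-tailed Fisher test gives power 0.801, and 90 is the smallest 2:1 total that reaches 0.80. The figure reproduces. (The Summary's "power=0.90, one-tailed Fisher's exact test", with α 0.05, does not: power at 90 is 0.877 and 96 patients are needed.)

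Under Table 6 the χ² test would apply. Expected beneficial outcomes are 30 × 0.269 + 60 × 0.597 = 43.9, so the smallest expected cell is 30 × 43.9/90 = 14.6. Exact power of χ² is 0.849.

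**2. Crude variance at 60+30, nodules above 10 mm.**

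0.731 × 0.269/30 + 0.403 × 0.597/60 = 0.01056, so SE = 0.1028.

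**3. Adjusting for the minimisation factors.** §8.2.2 gives malignancy odds ratios of 2.10 for size above 40 mm and 1.51 for male sex. Effects of Bethesda class and age are not given, so they are assumed.

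| Factors | Variance relative to crude (large-sample) |
|---|---|
| Size and sex only | 0.986 |
| Plus Bethesda 1.5 and age 1.5 (assumed) | 0.977 |
| Plus Bethesda 2.5 and age 2.0 (assumed) | 0.951 |

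The gain is therefore about 1 to 5%. In simulation at 90 patients the main-effects adjusted ratio was 1.00 to 1.04, so it may vanish. Read as conservatism of the crude test, the SE would be too large by 1/√0.986 = 1.007 to 1/√0.951 = 1.025, that is 0.7 to 2.5%.

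**4. Adjusting for PET in the ordinary way.** The split of the 75 unbeneficial outcomes into false positives and false negatives is not given for nodules above 10 mm. Let f be the false negatives, assumed 0 to 3 (3 is the all-sizes total in §1.3). Then FP = 75 − f, TN = 136 − FP = 61 + f, and PET-negatives = 61 + 2f. Write:

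- w = (61 + 2f)/186, the PET-negative fraction;
- c = (61 + f)/(61 + 2f), the control rate in PET-negatives;
- e = f/(61 + 2f), the experimental rate in PET-negatives;
- q = (75 − f)/(125 − 2f), the rate in PET-positives in either arm.

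Standardising the risk difference on PET gives variance ratios of 0.995 to 0.998. The reason is cancellation: PET-negativity raises the unbeneficial rate in controls (c − q = +0.35 to +0.40) and lowers it in the experimental arm (e − q = −0.56 to −0.60). A PET main effect without interaction raises variance by 12 to 14%. Mantel-Haenszel weighting by PET raises it by about 13% (all-sizes counts).

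**5. PET-negative contrast scaled by w.** If the arm effect in PET-positives is zero, the overall difference equals w(c − e), and the estimator's variance is

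w·c(1 − c)/30 + w·e(1 − e)/60 + (c − e)²·w(1 − w)/90.

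- f = 0: w = 0.328, c = 1, e = 0. Variance = 0.328 × 0.672/90 = 0.00245, SE 0.0495, ratio 0.232.
- f = 3: w = 0.360, c = 0.955, e = 0.045. Variance = 0.00077 + 0.00212 = 0.00289, SE 0.0538, ratio 0.274.

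Variance falls by 73 to 77%. In both cases w(c − e) = 0.328, the planned effect.

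A simulation on the all-sizes counts of Appendix IV (55 TP, 3 FN, 87 FP, 80 TN) agrees. The SE falls from 0.102 to 0.054 at 60+30 and from 0.084 to 0.044 at 88+44, a variance reduction of 72%. Both estimators centre on 0.342.

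**The case against.** The strongest defence is that nothing is broken. The sample size was computed for the unadjusted test and reproduces, and a crude test after minimisation errs on the safe side. Adjustment would not raise power materially, and a separate SAP may already contain an adjusted analysis. All of this stands, except that §10.3 fixes the primary comparison as crude and §10.4 as written does not correct it.

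Centre is a practical difficulty. Table 3 shows one of 15 centres with no patients and two with 2, so a fixed effect for each cannot be supported.

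The PET-negative contrast is also not free:

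- §11.2 plans the scan after randomisation, so PET is not strictly a baseline variable. A patient without a usable scan has no stratum, which sits badly with intention-to-treat.
- Identical management of PET-positives is planned, not guaranteed. §8.5 foresees patients who cannot follow the protocol, such as those found inoperable.
- §11.2 has the coordinating investigator review the images and send the instruction about surgery, whereas §3 blinds a review committee. Independence of the read from allocation should be confirmed.

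These points keep that contrast out of the primary position. They do not remove its value as support.

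A reader might infer that the plan throws away free precision, or that the crude test is invalid or leaves the trial underpowered. The figures above support none of these.

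**Conclusion.** The point holds as a mismatch between allocation and analysis, modest in size. The primary test ignores factors used to allocate patients, is valid, tends to be conservative and meets its planned power. Adjusting for the factors is right by design. Its expected return is about 1 to 5% of variance and possibly nil at 90 patients, given the protocol's two odds ratios and assumed effects for Bethesda class and age.

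The one large gain, roughly a halved standard error, belongs only to the scaled PET-negative contrast. It depends on no arm effect in PET-positives, a read blind to allocation, a rule for missing scans and the assumed 0 to 3 false negatives. A reader might expect ordinary PET stratification or adjustment to deliver it, but on the protocol's own counts it does not.

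**What to change.** Amend §10.3 before the unblinded final analysis:

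1. Make the primary estimate a standardised risk difference adjusted for ultrasound size, Bethesda class, age and sex. Pool small centres or fit centre as a random effect, dropped if the model does not converge. State whether centre was in fact a minimisation factor. Retain the Fisher/χ² test as sensitivity analysis.
2. Add as supportive, not primary, the comparison of PET-negative patients in arm A versus arm B as randomised, multiplied by the pooled PET-negative fraction.
3. For that analysis, state the assumption of no arm effect in PET-positives and check it by comparing their outcomes between arms. Confirm that the PET read was blind to allocation, and say how randomised patients without a usable scan are handled.
4. Do not use a PET main effect or Mantel-Haenszel weighting by PET for precision.

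The variables are already collected and nothing changes for patients. The cost is wording, a little more analysis, and reliance on the stated assumptions in the supportive result. The protocol records completed recruitment (§4.5) and an interim analysis on 17-04-2018 (§9.5), so the amendment should be dated and its timing relative to unblinding documented.
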